4.4. Study Days and Visits

For by-visit summaries, if there are multiple assessments at a postbaseline visit then the last non-missing assessment at that visit will be used for the summary (this includes scheduled and unscheduled assessments), except for triplicate ECG assessments (see Section 8.10 for further details).

Study visits are in Table 2 of the study protocol.

'Last Assessment' may be derived for analysis purpose and is defined as the last observed postbaseline data during the treatment period. For patients who withdraw from the study early, their data at the early withdrawal visit will be excluded from the by-visit summaries but will be included in the Last Assessment summaries.

Study days are numbered relative to the first day of the IMP administration. The start of treatment (day 1) is defined as the date on which a patient takes the first dose of the IMP, as

recorded on the case report form (CRF). Days will be numbered relative to treatment start (ie, ..., -2, -1, 1, 2, ...; with day 1 being the first day of the IMP administration and day -1 being the day before the first day of the IMP administration).

5. STUDY POPULATION

5.1. General

Study population summaries will be based on the ITT analysis set (see Section 3.1), unless otherwise specified. Summaries will be presented by treatment group and all patients. All data will be listed and sorted by treatment group and subject identifying number.

5.2. Patient Disposition

Data from patients screened, patients screened but not randomized, patients randomized to treatment in the study, patients randomized but not treated, patients in the ITT, mITT, safety and PP analysis sets and other analysis sets (Section 3), and patients who complete the double-blind treatment period and complete the study (see Section 2.1 for definitions of the double-blind treatment period and end of study) will be summarized. Data from screen failures, patients who did not complete the double-blind treatment period and patients who did not complete the study will also be summarized by reason for withdrawal using descriptive statistics.

This summary will include all patients.

5.3. Demographics and Baseline Characteristics

The demographic data will be collected at the screening visit after the patient signs the informed consent form. Patient demographic data including age, age group (<65 years vs \geq 65 years), gender, race, race group (white or other), ethnicity, baseline weight (kg), baseline height (cm), baseline body mass index (BMI; kg/m²), and baseline BMI group (<30 vs \geq 30), randomization stratification variables per IRT and per CRF: prior therapy (medium- and high-dose ICS alone and low-dose ICS/LABA vs. medium- and high-dose ICS/LABA), and absolute eosinophil count (300 to <400 cells/ μ L, or \geq 400 cells/ μ L) will be summarized using descriptive statistics for the ITT, safety, mITT, and PP analysis sets. In addition, baseline characteristics including asthma history and EGC findings at screening will be summarized for the ITT and safety analysis sets using descriptive statistics. No inferential analyses will be performed.

Asthma history includes

- Months since asthma diagnosis (derived)
- The duration of asthma
- The number of inpatient hospitalization due to asthma over the past 12 months
- Months since most recent inpatient event due to asthma (derived)
- The number of emergency department visit due to asthma over the past 12 months
- Months since most recent emergency department visit due to asthma (derived)
- the number of times oral or injectable corticosteroids were prescribed for asthma in the last 12 months
- Months since last prescription of oral corticosteroids for asthma (derived)

The month will be calculated as (date of informed consent - the date of the event + 1)/30.44. Rules for handling partial dates are in Section 4.3.

5.4. Medical History

All medical history abnormalities will be coded using the Medical Dictionary for Regulatory Activities (MedDRA). The incidence of medical history abnormalities will be summarized using descriptive statistics by system organ class (SOC) and preferred term. Patients are counted only once in each SOC and only once in each preferred term.

5.5. Prior Therapy and Medication

All prior medications or therapy will be coded using the World Health Organization Drug Dictionary of medical codes (WHO Drug). The incidence of prior medications or therapy will be summarized by therapeutic class and preferred term using descriptive statistics. Patients are counted only once in each therapeutic class category, and only once in each preferred term category. Prior medications will include all medications taken prior to the administration of the first dose of the IMP.

5.6. Childbearing Potential and Methods of Contraception

Information related to reproductive system findings will be collected at the screening visit. Data will be listed.

5.7. Study Protocol Deviations

Data from patients with any important protocol deviations during the study will be summarized overall and for each category using descriptive statistics. All study protocol deviations will be listed.

6. EFFICACY ANALYSIS

6.1. General

The mITT and PP analysis sets will be used for the efficacy analyses. The mITT analysis set will serve as the primary efficacy analysis population, while the PP analysis set will serve as the supportive population for the primary efficacy endpoint as well as the secondary efficacy endpoints.

Descriptive statistics (n, mean, standard deviation, standard error, median, minimum, and maximum for continuous variables, and patient counts and percentage for categorical variables) will be provided for each efficacy variable by visit or week, as appropriate. Summaries will be presented by treatment group.

Confidence/credible intervals will be provided at the two-sided 95% confidence level.

Unless otherwise specified, baseline value is defined as the last available value before the administration of IMP.

For the purpose of the efficacy analysis, the time point of “endpoint” will be derived and is defined as the last assessment during 16 weeks for a patient.

6.1.1. Analysis Windows and Baseline for Data Collected Daily

For data collected on e-diary and hand-held spirometry daily, the weekly analysis windows (week 1 to week 16) will be derived based on the study days as follows:

$$\text{Week } x: \text{day } (x-1)*7 + 1 \text{ to day } x*7$$

eg Week 1 is from days 1 to 7; Week 12 is days 78 to 84, etc.

Notes: Day 1 is the IMP administration date; for patients who withdraw from the study early, the last window may be less than 7 days.

The daily average of the efficacy data with each weekly analysis window will be calculated based on non-missing e-diary as follow:

$$\frac{\sum \text{an efficacy variable during an analysis window}}{\text{Number of days with nonmissing data in the analysis window}} \quad [1]$$

Baseline daily average for data collected daily will be calculated using the same formula above based on non-missing data.

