During the treatment period (baseline/day of randomization [DoR, V3] through week 16 [V9]), patients will perform morning lung function assessments (FEV₁ and PEF) by handheld device prior to morning asthma maintenance medication and prior to rescue medication use (whenever possible), assess and record daytime and night-time asthma symptom scores, record rescue medication use (number of puffs) twice daily and confirm (in the evening) that they have taken that day's asthma maintenance medication. During the treatment period visits, formal pulmonary function testing (as required) will be completed in the morning between 0530 and 1100±1 hour on the study-provided spirometry equipment. If a patient has taken rescue medication within 6 hours of the planned pulmonary function testing or has taken the morning dose of asthma maintenance medication, the testing should be cancelled, and the visit should be rescheduled. All formal pulmonary function testing should be conducted at approximately the same time of day ±1 hour of the time it was conducted at baseline/DoR (V3). Other procedures for each visit are outlined in [Table 2](#).

Patients who complete week 16 (end of treatment visit [EoTV; V9]) will enter the follow-up period. The handheld device and diary, along with study provided rescue medication will be collected. The investigator should determine and implement appropriate asthma therapy (including rescue treatment) to be used during the follow-up period. Medication started for the purpose of ongoing asthma treatment will not be considered a protocol violation, provided it is started after the final spirometry assessments are completed at week 16 (V9). Patients will be contacted approximately monthly by telephone to assess CAEs, adverse events, and concomitant medications. A final follow-up visit will occur at approximately week 30 for final assessments. A CAE is defined as worsening asthma requiring treatment with a systemic corticosteroid for ≥3 days, emergency room visit resulting in systemic corticosteroid treatment or hospitalization due to asthma. All instances of a CAE should be recorded in the CRF.

Alert criteria for individual patients who develop worsening asthma have been designed to ensure patient safety. If any of the criteria listed below are met, the investigator will determine whether the patient's overall clinical picture is consistent with worsening asthma and if the

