4.3. Randomization Criteria

The following criteria must be fulfilled at the randomization visit (day 0):

- a. The patient continues to be in general good health, meeting the entry criteria.
- b. The patient’s average of 5 most recent **highest** daily trough values (from 3 attempts) for morning FEV₁ obtained at home (by handheld spirometry) over 7 days prior to V3 is within 40% to 80% predicted for age, height, sex, and race ([Hankinson et al 1999](#), [Hankinson et al 2010](#), [NHANES III 1998](#)). If rescue medication was taken within 4 hours of the FEV₁ assessment, or asthma maintenance medication was taken before the measurement, the data from that day should be excluded and data from a previous day during the 7-day period should be included.
- c. The patient has an FEV₁ as assessed by clinic-based pulmonary function testing that is within 40% to 85% or the value predicted for age, height, sex, and race ([Hankinson et al 1999](#), [Hankinson et al 2010](#), [NHANES III 1998](#)).
- d. The patient has demonstrated FEV₁ reversibility as required during the screening period.
- e. The patient’s ACQ-6 score assessed on V3 day 0 is ≥ 1.5 .
- f. The patient has remained on background asthma maintenance medication without changes during the run-in period other than study rescue medication (albuterol eMDPI [ProAir Digihaler for use as needed or equivalent albuterol/salbutamol depending on availability]) and albuterol/salbutamol used for reversibility testing.
- g. The patient has had no exacerbation of asthma during the run-in period, defined as any worsening of asthma requiring significant treatment other than rescue medication (albuterol eMDPI [ProAir Digihaler for use as needed or equivalent albuterol/salbutamol depending on availability]). Significant treatment includes any of the following: use of systemic corticosteroids or the addition of ICS-containing asthma medications, LABA, long-acting muscarinic antagonist (LAMA), biologic or other non-corticosteroid asthma medications, emergency room/urgent care visit, or hospitalization for asthma. **Note: A single dose of nebulized albuterol/salbutamol will not meet the criteria for an asthma exacerbation. Emergency room/urgent**

care clinic visits where the treatment is limited to a single dose of nebulized albuterol/salbutamol will not meet the criteria of an asthma exacerbation.

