6.1.1. Pulmonary Function Testing

Pulmonary function testing (spirometry and reversibility testing) will be conducted in the morning between 0530 and 1100 during the screening period and V3, and 0530-1100±1 hour (subsequent visits) on study-provided spirometry equipment. Testing will be performed in the clinic unless specified as by handheld device, which will be provided to patients upon entering the run-in period for the assessment of lung function.

Lung function will be measured using standard spirometry consistent with ATS/ERS 2005 procedural guidelines ([Miller et al 2005](#)). The FEV₁ is the volume of air that can be forcibly exhaled from the lungs in the first second, measured in liters. The forced vital capacity (FVC) is the volume of air that can be forcibly blown out after full inspiration, measured in liters. The FEF₂₅₋₇₅ is the forced expiratory flow at 25% to 75% of FVC. The National Health and Nutrition Survey III reference equations ([NHANES III 1998](#)) will be used with adjustments for ethnicity ([Hankinson et al 1999](#), [Hankinson et al 2010](#)).

At the screening visit, FEV₁ will be measured immediately before and 30 (±15) minutes after administration of 4 inhalations of albuterol/salbutamol HFA MDI (90 µg ex-actuator) or equivalent. The spirometry equipment will provide the reversibility as a percent value. This value should not be rounded. FEV₁ reversibility ≥12% and a 200-mL increase from baseline FEV₁ is required.

The FEV₁ stability limit (clinic-based spirometry) will be calculated from each patient at the randomization visit (V3) using the following equation:

- best pre-albuterol/salbutamol FEV₁ × 80%

This value will be used for the remainder of the study and will be used to determine alert criteria for worsening asthma. The FEV₁ stability limit is automatically calculated and stored in the spirometry software. If a patient falls below the FEV₁ stability limit, an alert will be generated.

The FEV₁ stability limit for the handheld device will be 80% of the value obtained at the screening visit (using the clinic-based equipment value) and for the run-in period and 80% of the baseline value as determined by the handheld device for the treatment period.

FEV₁ and PEF in between visits will be measured using the handheld device (as above) each morning before the patient takes their asthma maintenance medication. Patients should avoid taking morning rescue medication within 6 hours of the measurement whenever possible. PEF is

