At this visit the patient's diary data should be reviewed prior to formal lung function testing, laboratory testing and the various questionnaires to ensure compliance with diary entries and to determine if lung function, symptoms and rescue medication use meet the randomization criteria. If the patient fails to meet the diary requirements, the patient will be considered a randomization failure. Further procedures for V3 will only be conducted for patients who meet the diary requirements.

The following procedures will be performed:

- review inclusion and exclusion criteria
- review randomization criteria
- review compliance with diary and study randomization requirements
- full physical examination (to include, at a minimum, head, eyes, ears, nose, and throat [HEENT], chest, cardiovascular, abdominal, skin, and neurological examination)
- pulmonary function testing (spirometry)
- hematology (CBC with differential analysis)
- fasting serum chemistry tests
- obtain a blood sample for Phadiatop Allergy Test and Total IgE
- obtain a blood sample for pharmacogenetics (confirm patient has provided informed consent for this procedure)
- obtain a blood sample for pharmacokinetics (serum IMP concentration)
- obtain a blood sample for serum anti-drug antibody (ADA) assay
- obtain a blood sample for biomarker interleukin 5 (IL-5) analysis
- urinalysis
- urine pregnancy test for women of childbearing potential (β HCG)
- 12-lead electrocardiogram (ECG) in triplicate. Each ECG will be taken within 1 to 5 minutes of the previous one.
- vital signs measurements
- [REDACTED]
- [REDACTED]
- complete ACQ-6
- Asthma Control Test (ACT)

- Standardized Asthma Quality of Life Questionnaire (AQLQ[S])
- [REDACTED]
- conduct training on handheld device and review diary use and compliance
- perform randomization and treatment assignment in interactive response technology (IRT) after confirming eligibility including diary and pulmonary function testing, ACQ 6 score and the remaining randomization criteria have been met.
- investigational medicinal product (IMP) dosing (Note: dosing may not occur until all clinical laboratory samples, and questionnaires have been completed). Doses will be administered by a qualified health care provider (according to local regulations) who is prepared to manage anaphylaxis
- postdose observation period of 1 hour
- injection site evaluation
- dispense rescue medication (if needed)
- collect rescue medication
- assess CAEs

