4.2. Specification of Baseline Values

Unless otherwise specified, baseline value is defined as the last observed value before the administration of IMP.

The baseline for hand-held spirometry parameters and e-diary variables will be the average of the values over the 7 days preceding day of randomization.

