The FEV₁ is measured by a handheld device daily. The weekly analysis window will be derived as described in Section 6.1.1. The daily average within each weekly analysis window will be

derived using formula [1] in Section 6.1.1. Measurement values taken within 4 hours of a rescue bronchodilator use will be set to missing.

The endpoints will be analyzed using a MMRM including baseline FEV₁, randomization stratification factors, week, treatment group, and week-by-treatment group interactions in the model with UN covariance structure. In the case UN covariance structure does not converge, the compound symmetry (CS) covariance structure will be used.

One MMRM model will be run including all 16-week data. The overall and by-week results will be derived using appropriate contrast statements and presented. The endpoint will be measured by the overall results. LS mean and SE for each treatment group, LS means and corresponding 95% confidence intervals for the treatment differences (active - placebo), and the associated p-values from the overall results for treatment comparisons.

Descriptive statistics from each week will be provided.

[REDACTED]

6.3.3. Overall Changes from Baseline in Weekly Average of Rescue Medication Use Over 12 Weeks From Week 1 Through 12 and Over 16 Weeks From Week 1 Through 16

The number of times asthma rescue medication (number of inhalations/puffs) used will be recorded on e-diary.

The post-baseline analysis window for over 12 weeks will be from the first day of IMP up to the day 84. The post-baseline analysis window for over 16 weeks will be from the first day of IMP up to the day 112. Baseline window will include days up to the first dose of IMP. Data in each analysis window will be normalized to 7 days as

$$(\sum \text{rescue medication uses during an analysis window} / \text{number of non-missing e-diary days during the analysis window}) * 7$$

The changes from baseline in weekly average of rescue medication over week 12 and over week 16 will be calculated and analyzed using Wilcoxon rank-sum test stratified on randomization stratification factors, respectively. The Hodges-Lehmann estimator of the treatment differences (TEV43275 treatment groups vs placebo) will be presented.

[REDACTED]

[REDACTED]

[REDACTED]

[REDACTED]

[REDACTED]

[REDACTED]

[REDACTED]

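### SAP 6.1.1 counts the dosing-day morning handheld FEV1, taken before the injection, as Week 1 response, and SAP 6.3.3 and 6.3.4 leave Day 1 diary entries open to either window

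*SAP*

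**What the plan says.** **Windows for daily data (SAP 6.1.1).** The weekly windows are "eg Week 1 is from days 1 to 7; Week 12 is days 78 to 84, etc". The note to the formula adds: "Notes: Day 1 is the IMP administration date". The text does not separate entries made before the injection from those made after it. The only handheld exclusion visible in SAP 6.3.2 concerns readings taken within 4 hours of rescue bronchodilator use.

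**Baseline (SAP 4.2).** "The baseline for hand-held spirometry parameters and e-diary variables will be the average of the values over the 7 days preceding day of randomization". The dosing-day record is therefore outside baseline.

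**Rescue use and asthma control days (SAP 6.3.3, 6.3.4).** Post-baseline starts on the first day of IMP. For baseline, both sections say: "Baseline window will include days up to the first dose of IMP". Neither gives a start day for baseline.

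**Timing (protocol).**
- Section 3.1 has daily recording "During the treatment period (baseline/day of randomization [DoR, V3] through week 16 [V9"]), so a dosing-day entry is expected.
- Section 6.1.1 has handheld FEV1 measured "each morning before the patient takes their asthma maintenance medication".
- Section 6.1.5 has the night-time symptom score determined in the morning.
- The footnotes to Table 2 hold back randomization until lung function, questionnaires and clinical assessments are finished.
- Appendix B adds that "dosing may not occur until all clinical laboratory samples, and questionnaires have been completed".

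**Clinic spirometry (SAP Table 1).** The first window admits Day 1 values only after the dose.

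**The concern.** A value recorded before the injection cannot show a drug effect. Counting it as response adds a reading with an expected treatment difference of zero and pulls the arms together.

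Three sets of results are exposed:
- **Week 1 handheld FEV1**, because SAP 6.3.2 presents by-week as well as overall results.
- **Week 1 asthma control status**, because SAP 6.3.1 requires a week with no night-time awakenings, so one awakening on the night before dosing makes the week a No. All weekly statuses enter the logistic model.
- **Rescue use and asthma control days**, where the text does not settle whether a pre-dose Day 1 entry is baseline or response.

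The SAP makes the pre-dose distinction for clinic data, so its absence for daily data looks like an oversight.

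**Working it through.** **1. Order of events on the dosing date.** Morning handheld FEV1 and night-time score come first. Clinic spirometry, samples and questionnaires follow, then randomization, then the injection. The daytime score is entered in the evening, after the injection. The morning entries are therefore pre-dose and the evening entry is made post-dose.

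**2. The SAP windows, reproduced.** Week x runs from day (x−1)×7+1 to day x×7.
- Week 1: 0×7+1 = 1 to 7.
- Week 12: 11×7+1 = 78 to 84.
- Week 16: 15×7+1 = 106 to 112.

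These match the SAP's examples for Weeks 1 and 12.

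**3. Weight of the pre-dose reading.** Formula [1] in SAP 6.1.1 divides by the number of non-missing days.
- Week 1, 7 days recorded: 1/7 = 14.3%. With 5 days recorded: 1/5 = 20%. With 3: 1/3 = 33%.
- Weeks 1-12, complete diary: (1/12)×(1/7) = 1/84 = 1.2%.
- Weeks 1-16, complete diary: (1/16)×(1/7) = 1/112 = 0.9%.

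**4. What that does to an effect.** Assume a constant difference of 0.10 L from the first post-dose morning. This borrows the base-case effect in SAP 2.4, which is for the clinic endpoint.
- Week 1: 0.10×6/7 = 0.086 L.
- Weeks 1-12: 0.10×83/84 = 0.0988 L.
- Weeks 1-16: 0.10×111/112 = 0.0991 L.

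**5. The awakening criterion in Week 1.** Assume that the night-time score belongs to its recording date and that nights are independent. Let the awakening probability be p0 before dosing and p1 after it.
- Awakening-free week as now defined: (1−p0)(1−p1)^6.
- Seven post-dose nights: (1−p1)^7.
- Relative loss: 1 − (1−p0)/(1−p1).

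The documents give no awakening rates. For assumed p0 = 0.2 and p1 = 0.1 the loss is 1 − 0.8/0.9 = 11%. Where p1 = p0 it is zero.

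For an active arm with those values, and a placebo arm staying at 0.2:

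| Nights counted in Week 1 | Active | Placebo | Difference |
|---|---|---|---|
| 1 pre-dose + 6 post-dose (now) | 0.8×0.9^6 = 0.425 | 0.8^7 = 0.210 | 0.215 |
| 6 post-dose | 0.9^6 = 0.531 | 0.8^6 = 0.262 | 0.269 |

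The difference on this one criterion is about 20% smaller under the present rule (1 − 0.215/0.269), in Week 1 only.

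**6. Day 1 in SAP 6.3.3 and 6.3.4.** Post-baseline includes the whole dosing date. Baseline runs up to the first dose, which can take in the hours of that date before the injection. SAP 4.2 stops the day before. A Day 1 morning entry can thus be placed in either window.

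**The case against.** **The listed endpoints hardly move.** This stands. The secondary endpoints are overall results for weeks 1-12 and 1-16, shifted by about 1%, and SAP 6.3.2 says the overall result is the measure. Week 1 results are secondary output.

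**The night-time score may belong to the previous day.** The SAP does not say. If it does, the awakening argument falls away and the FEV1 point remains.

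**A Day 1 reading may not exist, or may be filtered in code.** Protocol 6.1.1 describes handheld readings as taken between visits, but section 3.1 includes the day of randomization. Analysis code is redacted, so a pre-dose filter cannot be ruled out; no visible text states one.

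**SAP 4.2 could be read as governing.** It would then keep Day 1 out of baseline in 6.3.3 and 6.3.4. That is a fair reading, but those sections give their own baseline wording, so the two need reconciling.

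**Stronger readings that the documents do not support:**
- *That the extra night costs 10% to 30% of Yes weeks in every arm.* This comes from comparing seven nights with six at a constant p (at p = 0.1, 0.478 against 0.531). It measures the length of the window, not the pre-dose night. With p constant, replacing the pre-dose night with a post-dose one changes nothing.
- *That the requirement of FEV1 of at least 80% predicted on each day spoils Week 1 because of this window.* Randomization required a handheld mean "over 7 days prior to V3 is within 40% to 80% predicted for age, height, sex, and race", so the requirement is hard to meet on Days 2-8 too. It is also one of three criteria, of which two suffice.
- *That all daily windows should move to Days 2-8.* This would leave the Day 1 evening entry, made after dosing, in no window. Week 16 would end on Day 113, the nominal V9 day, when diary and device are collected.

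**Conclusion.** The point holds. As written, SAP 6.1.1 classifies a pre-injection handheld FEV1 as Week 1 response, and SAP 6.3.3 and 6.3.4 leave pre-dose Day 1 diary entries unassigned. The direction is toward no difference.

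The size is modest: up to 14% of the Week 1 handheld mean with a full diary, and about 1.2% and 0.9% of the 12- and 16-week averages. For Week 1 control status, the loss on the awakening criterion depends on how far the nightly risk changes after dosing: 11% in an arm going from an assumed 0.2 to 0.1, and none where it is unchanged.

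This rests on a handheld reading being taken on the dosing morning, on no pre-dose filter in redacted code and, for the awakening part only, on the score being assigned to its recording date. The primary endpoint uses clinic spirometry at week 12 and is not affected. A reader should not infer a material loss on any listed endpoint.

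**What to change.** Keep the Day 1-7 windows and amend the SAP before unblinding:

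1. In 6.1.1, count only post-dose Day 1 entries in Week 1, as Table 1 does for clinic data. Exclude the Day 1 morning handheld FEV1 and the Day 1 morning diary entry (night-time score, overnight rescue use) from post-baseline.
2. State which study day the night-time score belongs to.
3. In 6.3.3 and 6.3.4, apply the same Day 1 rule and replace the baseline sentence with the 7-day baseline of SAP 4.2. Say how a Day 1 with only its evening entry counts in the number of diary days.

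**Cost.** A few lines of text and matching programming; no new data. Week 1 then has at most six morning values, so its mean is slightly less precise and its control status is judged on six nights in every arm. The Day 1 evening entry still covers some hours before the injection; this is a small remainder that can be accepted.
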